5.1. Formulation of Envarsus

Similar to tacrolimus, Envarsus is a macrolide antibiotic. It has a unique drug delivery technology designed to enhance the bioavailability. The technology breaks the drug particles down into the smallest possible units, which are then sprayed onto a carrier, forming a granulate, and then compressed into tablets with a stable dissolution profile and particle size. The smaller drug particle size creates greater drug surface area and greater absorption.

5.2. Dosage, Preparation, and Administration

5.2.1. Dosage

Envarsus pills come in 0.75 mg, 1 mg and 4 mg concentration tablets

5.2.2. Conversion Plan

Patients will convert from current tacrolimus dose to an Envarsus dose that is 80% of the total tacrolimus dose. They will take Envarsus once daily in the morning and have 24-hour trough levels monitored at the standard of care interval for tacrolimus. Dosing will be titrated to achieve goal levels.

5.3. Premature Discontinuation of Envarsus

Envarsus will be stopped and will not be restarted if there is a hypersensitivity reaction, a CTCAE >2, CRS or any serious adverse event.

6. Other Medications

6.1. Immunosuppressive Medications

6.1.1. Tacrolimus

Target tacrolimus trough levels for this study are standard of care at the transplant center, 8-12 ng/mL the first 6 months post transplant and 6-9 ng/mL post-transplant months 7-12.

6.1.2 Mycophenolate Mofetil (MMF)/ Mycophenolic Acid (MPA)

All enrolled subjects will be on MMF/MPA at the time of study entry at a minimum dose of 1000 mg/720 mg per day. Once subjects are enrolled in the study, doses may be adjusted at the discretion of the study investigator for gastrointestinal intolerance, cytopenias, infections or other conditions that require dose adjustment. All mycophenolate prescribers in the study will be required to enroll in the FDA mycophenolate REMS (risk evaluation and mitigation strategy) program.

6.1.3 Prednisone

Use of corticosteroids is standard of care at the center and considered part of the treatment regimen in this trial.

6.1.4 Other Immunosuppressive Medications

Patients requiring the use of azathioprine or mTOR inhibitors will not be enrolled in this study.

6.2. Anti-Infective Prophylactic Medications

Anti-infective prophylaxis medications will be per standard of care.

6.3. Prohibited Medications

6.3.1. Vaccinations

The use of live vaccines will be prohibited during trial participation, as per standard of care for kidney transplant recipients. Examples include (but are not limited to) the following: intranasal influenza, measles, mumps, rubella, oral polio, BCG, yellow fever, varicella, and TY21a typhoid vaccines. Subjects should not receive any vaccination (live or inactivated) within 5 days prior to study enrollment.

6.3.2. Medication Interactions

Administration of medications known to interact with tacrolimus and cyclosporine metabolism are allowed but tacrolimus and cyclosporine levels should be carefully monitored, and dosing titrated to maintain the target levels to minimize toxicity while maintaining efficacy.

6.4. Treatment of Rejection

Patients who are clinically suspected to have a rejection will undergo a kidney biopsy as part of their standard of care. Biopsies will be read locally according to the

Banff criteria and if acute rejection is diagnosed, it will be treated according to the current standard of care.

7. Standard Care Procedures While On Study

7.1. Blood Draws

Blood draws are necessary after kidney transplantation to monitor allograft function.

7.2. Kidney Biopsy

Study participants will have an allograft biopsy performed for medical indications such as allograft dysfunction or proteinuria and these results analyzed by an experienced renal pathologist. Patients may undergo a routine surveillance biopsy per institutional protocol.

8. Known and Potential Risks and Benefits to Participants

8.1. Risks of Envarsus

The most common adverse reactions to treatment with Envarsus are similar to the adverse reactions listed below with tacrolimus.

8.2. Risks of Tacrolimus and Mycophenolate Mofetil/Mycophenolic Acid

Subjects will be on tacrolimus and mycophenolate at the time of study entry. Potential risks applicable to their use in this study are listed below.

8.2.1. Risks of Tacrolimus

Post-Transplant Diabetes Mellitus: Insulin-dependent post-transplant diabetes mellitus (PTDM) was reported in 20% of tacrolimus-treated kidney transplant patients without pre-transplant history of diabetes mellitus in the Phase III study. The median time to onset of PTDM was 68 days. Insulin dependence was reversible in 15% of these PTDM patients at one year and in 50% at 2 years post- transplant. Black and Hispanic kidney transplant patients were at an increased risk of development of PTDM.

Nephrotoxicity: Tacrolimus can cause nephrotoxicity, particularly when used in high doses. Nephrotoxicity was reported in approximately 52% of kidney transplantation patients and in 40% and 36% of liver transplantation patients receiving tacrolimus in the U.S. and European randomized trials, respectively, and in 59% of heart transplantation patients in a European randomized trial. In patients with persistent elevations of serum creatinine who are unresponsive to dosage adjustments, consideration should be given to changing to another immunosuppressive therapy. Care should be taken in using tacrolimus with other nephrotoxic drugs.

Hyperkalemia: Mild to severe hyperkalemia was reported in 31% of kidney transplant recipients and in 45% and 13% of liver transplant recipients treated with tacrolimus in the U.S. and European randomized trials, respectively, and in 8% of heart transplant

recipients in a European randomized trial and may require treatment. Serum potassium levels should be monitored and potassium-sparing diuretics should not be used during tacrolimus therapy.

Neurotoxicity: Tacrolimus can cause neurotoxicity, particularly when used in high doses. Neurotoxicity, including tremor, headache, and other changes in motor function, mental status, and sensory function were reported in approximately 55% of liver transplant recipients in the two randomized studies. Tremor occurred more often in tacrolimustreated kidney transplant patients (54%) and heart transplant patients (15%) compared to cyclosporine-treated patients. The incidence of other neurological events in kidney transplant and heart transplant patients was similar in the two treatment groups. Tremor and headache have been associated with high whole-blood concentrations of tacrolimus and may respond to dosage adjustment. Seizures have occurred in adult and pediatric patients receiving tacrolimus. Coma and delirium also have been associated with high plasma concentrations of tacrolimus. Patients treated with tacrolimus have been reported to develop posterior reversible encephalopathy syndrome (PRES). Symptoms indicating PRES include headache, altered mental status, seizures, visual disturbances and hypertension. Diagnosis may be confirmed by radiological procedure. If PRES is suspected or diagnosed, blood pressure control should be maintained and immediate reduction of immunosuppression is advised. This syndrome is characterized by reversal of symptoms upon reduction or discontinuation of immunosuppression.

Malignancy and Lymphoproliferative Disorders: As in patients receiving other immunosuppressants, patients receiving tacrolimus are at increased risk of developing lymphomas and other malignancies, particularly of the skin. The risk appears to be related to the intensity and duration of immunosuppression rather than to the use of any specific agent. A lymphoproliferative disorder (LPD) related to Epstein-Barr Virus (EBV) infection has been reported in immunosuppressed organ transplant recipients. The risk of LPD appears greatest in young children who are at risk for primary EBV infection while immunosuppressed or who are switched to tacrolimus following long-term immunosuppression therapy. Because of the danger of oversuppression of the immunosuppressant therapy should be used with caution.

Latent Viral Infections: Immunosuppressed patients are at increased risk for opportunistic infections, including activation of latent viral infections. These include BK virus associated nephropathy and JC virus associated progressive multifocal leukoencephalopathy (PML) which have been observed in patients receiving tacrolimus. These infections may lead to serious, including fatal, outcomes.

8.2.2. Risks of Mycophenolate Mofetil/ Mycophenolic Acid

Embryofetal Toxicity: Mycophenolate mofetil (MMF) can cause fetal harm when administered to a pregnant female. Use of MMF during pregnancy is associated with an increased risk of first trimester pregnancy loss and an increased risk of congenital

malformations, especially external ear and other facial abnormalities including cleft lip and palate, and anomalies of the distal limbs, heart, esophagus, kidney and nervous system.

All prescribers at this center have already been enrolled in the MMF REMS program. Of note, all study participants will already have been on a maintenance regimen containing MMF/MPA and will not be started on it as part of the study. All females must be willing to use FDA approved methods of birth control acceptable during the entire period of the study.

For those females who are discovered to be pregnant either at study screening or enrollment or during the study and who are on MMF/MPA or within 6 weeks of discontinuing therapy, the study investigators will report the pregnancy to the Mycophenolate Pregnancy registry ([name]) and strongly encourage the patient to enroll in the pregnancy registry. When appropriate, pregnant patients will be switched to alternative immunosuppression with less potential for embryo-fetal toxicity after a discussion of maternal and fetal risks and benefits.

Lymphoma and Malignancy: Patients receiving immunosuppressive regimens involving combinations of drugs, including MMF, as part of an immunosuppressive regimen are at increased risk of developing lymphomas and other malignancies, particularly of the skin. The risk appears to be related to the intensity and duration of immunosuppression rather than to the use of any specific agent. As usual for patients with increased risk for skin cancer, exposure to sunlight and UV light should be limited by wearing protective clothing and using a sunscreen with a high protection factor. Lymphoproliferative disease or lymphoma developed in 0.4% to 1% of patients receiving MMF (2 g or 3 g) with other immunosuppressive agents in controlled clinical trials of renal, cardiac, and hepatic transplant patients. In pediatric patients, no other malignancies besides lymphoproliferative disorder (2/148 patients) have been observed.

Combination with Other Immunosuppressive Agents: MMF has been administered in combination with the following agents in clinical trials: antithymocyte globulin (ATGAM[®]), OKT3 (Orthoclone OKT[®] 3), cyclosporine (Sandimmune[®], Neoral[®]), tacrolimus (Prograf[®]), and corticosteroids. The efficacy and safety of the use of MMF in combination with other immunosuppressive agents have not been determined.

Serious Infections: Patients receiving immunosuppressants, including MMF, are at increased risk of developing bacterial, fungal, protozoal and new or reactivated viral infections, including opportunistic infections. These infections may lead to serious, including fatal outcomes. Because of the danger of over suppression of the immune system which can increase susceptibility to infection, combination immunosuppressant therapy should be used with caution.

New or Reactivated Viral Infections: Polyomavirus associated nephropathy (PVAN), JC virus associated progressive multifocal leukoencephalopathy (PML), cytomegalovirus (CMV) infections, reactivation of hepatitis B (HBV) or hepatitis C (HCV) have been reported in patients treated with immunosuppressants, including MMF. Reduction in immunosuppression should be considered for patients who develop evidence of new or reactivated viral infections. Physicians should also consider the risk that reduced immunosuppression represents to the functioning allograft. PML, which is sometimes fatal, commonly presents with hemiparesis, apathy, confusion, cognitive deficiencies, and ataxia. Risk factors for PML include treatment with immunosuppressant therapies and impairment of immune function. In immunosuppressed patients, physicians should consider PML in the differential diagnosis in patients reporting neurological symptoms and consultation with a neurologist should be considered as clinically indicated. The risk of CMV viremia and CMV disease is highest among transplant recipients seronegative for CMV at time of transplant who receive a graft from a CMV seropositive donor. Therapeutic approaches to limiting CMV disease exist and should be routinely provided. Patient monitoring may help detect patients at risk for CMV disease. Viral reactivation has been reported in patients infected with HBV or HCV. Monitoring infected patients for clinical and laboratory signs of active HBV or HCV infection is recommended.

Neutropenia: Severe neutropenia [absolute neutrophil count (ANC) <0.5 x $10^3/uL$] developed in up to 2.0% of renal, up to 2.8% of cardiac, and up to 3.6% of hepatic transplant patients receiving MMF 3g daily. Patients receiving MMF should be monitored for neutropenia. The development of neutropenia may be related to MMF itself, concomitant medications, viral infections, or some combination of these causes. If neutropenia develops (ANC <1.3 x $10^3/uL$), dosing with MMF should be interrupted or the dose reduced, appropriate diagnostic tests performed, and the patient managed appropriately. Neutropenia has been observed most frequently in the period from 31 to 180 days post-transplant in patients treated for prevention of renal, cardiac, and hepatic rejection. Patients receiving MMF should be instructed to report immediately any evidence of infection, unexpected bruising, bleeding or any other manifestation of bone marrow depression.

Pure Red Cell Aplasia (PRCA): Cases of pure red cell aplasia (PRCA) have been reported in patients treated with MMF in combination with other immunosuppressive agents. The mechanism for MMF induced PRCA is unknown; the relative contribution of other immunosuppressants and their combinations in an immunosuppression regimen are also unknown. In some cases, PRCA was found to be reversible with dose reduction or cessation of MMF therapy. In transplant patients, however, reduced immunosuppression may place the graft at risk.

Gastrointestinal Disorders: Gastrointestinal bleeding (requiring hospitalization) has been observed in approximately 3% of renal, in 1.7% of cardiac, and in 5.4% of hepatic transplant patients treated with MMF 3 g daily. In pediatric renal transplant patients, 5/148 cases of gastrointestinal bleeding (requiring hospitalization) were observed.

Gastrointestinal perforations have rarely been observed. Most patients receiving MMF were also receiving other drugs known to be associated with these complications. Patients with active peptic ulcer disease were excluded from enrollment in studies with MMF. Because MMF has been associated with an increased incidence of digestive system adverse events, including infrequent cases of gastrointestinal tract ulceration, hemorrhage, and perforation, MMF should be administered with caution in patients with active serious digestive system disease.

Patients with Renal Impairment: Subjects with severe chronic renal impairment (GFR <25 mL/min/1.73 m²) who have received single doses of MMF showed higher plasma MPA and MPAG AUCs relative to subjects with lesser degrees of renal impairment or normal healthy volunteers. No data are available on the safety of long-term exposure to these levels of MPAG. Doses of MMF greater than 1 g administered twice a day to renal transplant patients should be avoided and they should be carefully observed.

Patients with HGPRT Deficiency: MMF is an IMPDH (inosine monophosphate dehydrogenase) inhibitor; therefore, it should be avoided in patients with rare hereditary deficiency of hypoxanthine-guanine phosphoribosyl-transferase (HGPRT) such as Lesch-Nyhan and Kelley-Seegmiller syndrome.

Phenylketonurics: MMF Oral Suspension contains aspartame, a source of phenylalanine (0.56 mg phenylalanine/mL suspension). Therefore, care should be taken if MMF Oral Suspension is administered to patients with phenylketonuria.

8.3. Risks of Standard Care Procedures While On Study 8.3.1. Risks of Blood Draws

Risks of blood draw or venipuncture are typically minimal with temporary local discomfort. More serious risks would include ecchymosis and, rarely, localized infection.

8.3.2. Risks of Kidney Biopsy

There is a risk of bleeding associated with transplant kidney biopsies. Transient hematuria occurs in 3 to 10% of patients and may prolong hospitalization, require bladder catheterization for clot drainage, or in approximately 1% of patients, require blood transfusion. Ureteral obstruction from blood clot may require percutaneous nephrostomy in <1% of patients. Massive hemorrhage requiring surgical exploration, transplant nephrectomy, or arterial embolization occurs in approximately 0.1 % of patients. Death from massive hemorrhage is rare.

8.4. Potential Benefits

This study might not provide direct or immediate benefit to the participants, but it is hoped that the information gained may benefit future kidney transplant patients.

8.4.1. Decrease in BK Infection

It is possible that use of Envarsus in place of tacrolimus will reduce incidence of

BK viruria, viremia, and nephropathy.

8.4.2. Prolongation in Graft Survival

The reduced incidence of BK infection may result in improved graft function and ultimately survival. It is difficult to predict the magnitude of this effect and it may not be apparent for months or years after treatment.

9. Study Visits

9.1. Enrollment

The research study will be explained in lay terms to each potential research participant. The potential participant will sign an informed consent form before undergoing any study procedures. A participant is considered enrolled in the trial once the consent form has been signed.

9.2. Follow - Up Visits

The initial visit and subsequent visits on study days 30, 120, 210, and 300 will include routine evaluation with physical examination and laboratory studies. These laboratory studies include BK urine and serum testing, CBC, renal function panel, eGFR, CNI and MPA drug levels, urinalysis, donor specific antibody testing, and urine protein/creatinine ratio according to the center's standard of care.

Please refer to Appendix 1 for schedule of events.

9.3. Unscheduled Visits

If creatinine increases or other concerns arise between regularly scheduled visits, participants will return to the study site for an "unscheduled" visit.

9.4. Visit Time Frames/ Windows

Study visits should take place within the time frames specified below in Table 1. The designated visit windows for each scheduled study visit are indicated in Appendix 1 Schedule of Events.

Visit No.	Study Visit Label	Time Frame Post Transplant
Screen	Study Eligibility	Approximately 1 month
1	Enrollment Day 0/ Visit 1	Approximately 2 months
2	Study Day 30/ Visit 2	Approximately 3 months
3	Study Day 120/ Visit 3	Approximately 6 months
4	Study Day 210/ Visit 4	Approximately 9 months
5	Study Day 300/ Visit 5	Approximately 12 months

10. Criteria for Participant Completion and Premature Study Termination

Participants may be prematurely terminated from the study for the following reasons:

- The participant elects to withdraw consent from all future study activities, including follow-up.
- The participant is "lost to follow-up" 3 months after the date of a missed study visit (i.e., no further follow-up is possible because attempts to reestablish contact with the participant have failed).
- The participant dies.
- The Investigator no longer believes participation is in the best interest of the participant.
- CTCAE Grade 3 or higher drug-related reaction
- A decision is made by the investigators and/or study supporter to stop the study

11. Safety Monitoring and Reporting

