3.1. Description of Study Design

This will be a single center prospective case control study. We expect 40% of patients will develop BK viruria, 20% BK viremia, 5% BK viral nephropathy (BKVN). Patients will be managed using standard of care for our center (thymoglobulin induction, tacrolimus/mycophenolate/prednisone). Target tacrolimus level is 8-12 ng/mL for the first 6 months post transplant and 6-9 ng/mL thereafter. BK urine/serum is routinely monitored during the first year post transplant. A population of 100 patients is calculated to show significant difference for p value < 0.05.

Population:

Study Group: Post transplant patients (kidney transplant alone) with standard of care immunosuppression, no prior rejection, prior BK or opportunistic infection, and negative BK screening at post-transplant month 1, who have a tacrolimus concentration/dose of < 1 and a steady state therapeutic level will be eligible. Patients who consent to participate will be converted to Envarsus at 20% reduction in tacrolimus dose.

Control Group: Post transplant patients (kidney transplant alone performed between 10-2016 and time of consideration for study control group) with standard of care immunosuppression, no prior rejection, prior BK or opportunistic infection, who had a negative BK screening at post-transplant month 1 and tacrolimus concentration/dose of < 1 at post-transplant month 1, and BK data available for months 2, 3, 6, 9, 12 post transplant.

Study visits: Post-transplant Months 2, 3, 6, 9, 12

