11.4. Collection and Recording of Adverse Events 11.4.1. Collection Period

Adverse events will be collected from the time of first study mandated activity

until a subject completes study participation or until 30 days after he/she prematurely withdraws (without withdrawing consent), or is withdrawn from the study.

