11.4.3. Recording Adverse Events

Throughout the study, the investigator will record adverse events and serious adverse events as described previously (Section 14.2, *Definitions*) on the appropriate AE/SAE form regardless of the relationship to study therapy regimen or study procedure.

Once recorded, an AE/SAE will be followed until it resolves with or without sequelae, or until the end of study participation, or until 30 days after the subject prematurely withdraws (without withdrawing consent)/or is withdrawn from the study, whichever occurs first.

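### A drug-related grade 3 or higher reaction should stop Envarsus, not follow-up: Section 10 lets it end participation, which can lose BK PCR results in the Envarsus group only

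*Combined protocol and SAP*

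**What the plan says.** Section 10 opens its list with "Participants may be prematurely terminated from the study for the following reasons", and one item is a "CTCAE Grade 3 or higher drug-related reaction". The wording is permissive, but what it permits is the end of study participation, not only of treatment.

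Stopping the drug is covered separately in Section 5.3: "Envarsus will be stopped and will not be restarted if there is a hypersensitivity reaction, a CTCAE >2, CRS or any serious adverse event".

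After an early exit, the stated collection concerns adverse events. Section 11.4.1 collects them "until 30 days after he/she prematurely withdraws" or is withdrawn, and Section 11.4.3 follows recorded events to resolution, the end of participation, "or until 30 days after the subject prematurely withdraws (without withdrawing consent)/or is withdrawn from the study, whichever occurs first". No section plans to record BK results after exit.

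Controls are historical (Section 12), and Section 3.1 admits them only with "BK data available for months 2, 3, 6, 9, 12 post transplant". BK testing is part of usual care: Section 3.1 says "BK urine/serum is routinely monitored during the first year post transplant", and Section 9.2 says of the standard-of-care visits "These laboratory studies include BK urine and serum testing".

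Section 12 summarises reasons for early termination. It defines no analysis set and no rule for missing outcomes.

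**The concern.** The primary endpoint (Section 3.3) is a composite of viruria, viremia or nephropathy, and the first two components depend on serial PCR through month 12. A patient who leaves follow-up while BK-negative has an unknown outcome. The plan does not say whether that patient counts as event-free, counts as an event, or is dropped.

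The exit can occur in one group only. A historical control cannot be removed from the study, and has complete scheduled BK data by selection. Section 11.3.2 also limits attribution of adverse events to Envarsus. Because the treatment is open and the rule discretionary, who leaves follow-up is decided case by case.

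The point is narrow. It does not cover nephropathy, which needs a biopsy and can go unobserved in either group. Nor does it cover the other Section 10 exits, such as death, consent withdrawal and loss to follow-up. Those are largely unavoidable; this one is not.

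**Working it through.** The plan gives no figure to reproduce on this point. The check is a comparison of sections, then arithmetic for scale.

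**1. What the Section 10 item adds**

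| Event: drug-related reaction, CTCAE grade 3 or higher | Section 5.3 | Section 10 |
|---|---|---|
| Envarsus stopped | Yes, permanently | Not needed |
| Participation may end | No | Yes |
| BK results planned afterwards | Yes, if still in the study (9.2, Appendix 1) | No; adverse events only, up to 30 days (11.4.1, 11.4.3) |

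The only additional effect of the Section 10 item is the loss of planned follow-up.

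**2. Which group it can touch**

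Controls have BK data at months 2, 3, 6, 9 and 12 as a condition of entry (3.1) and cannot be withdrawn. Missing BK PCR results from this rule can therefore arise only in the Envarsus group.

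**3. Scale of the uncertainty**

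Let n be the number of Envarsus patients, x the known events (including any before exit), and k the leavers still BK-negative at exit. A leaver already positive is a known event and is not in k.

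- All k counted as BK-free: x/n
- All k counted as BK-positive: (x + k)/n
- Spread: k/n

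Section 3.1 gives a population of 100 but no group split, so n = 50 and n = 100 are both assumed:

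| k | n = 50 | n = 100 |
|---|---|---|
| 1 | 2 points | 1 point |
| 3 | 6 points | 3 points |
| 5 | 10 points | 5 points |

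If five patients leave and two were already positive, k = 5 − 2 = 3, and the spread at n = 50 is 3/50 = 6 points.

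**4. Could it change a conclusion?**

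The counts below are all assumed: controls 20/50, x = 9, k = 3, 50 Envarsus patients. P-values are two-sided Fisher exact.

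| Handling of the three leavers | Envarsus | p |
|---|---|---|
| Counted BK-free | 9/50 = 18.0% | 0.0266 |
| Excluded | 9/47 = 19.1% | 0.0286 |
| Counted BK-positive | 12/50 = 24.0% | 0.1328 |

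These counts were chosen near the threshold. With controls at 20/50 and k = 3, moving from the BK-free to the BK-positive assumption crosses 0.05 only when x is 8, 9 or 10:

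| x | p at x/50 | p at (x + 3)/50 |
|---|---|---|
| 7 | 0.0063 | 0.0486 |
| 8 | 0.0135 | 0.0828 |
| 9 | 0.0266 | 0.1328 |
| 10 | 0.0486 | 0.2016 |
| 11 | 0.0828 | 0.2912 |

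This shows that the handling can matter. It does not forecast that it will.

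**The case against.** The strongest case against runs as follows. The clause is permissive and its trigger is narrow: the event must be grade 3 or higher and drug-related. Infections are graded on a separate scale (11.3.1), so BK infection does not obviously trigger it. Participants already take tacrolimus, and Section 8.1 describes the common reactions to Envarsus as similar, so nothing shows that k would exceed zero or one. Sections 11.4.1 and 11.4.3 are safety rules; they do not forbid taking BK results from the chart, where routine testing would usually have left them. The deeper causes are the complete-data requirement for controls and the lack of an analysis set in Section 12. Finally, deleting the item leaves the investigator's best-interest exit, which could remove the same patient.

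Much of this stands as a limit on size. The frequency is unknown, the number affected may be small, and excluding three leavers in the illustration barely moves the p-value. The objection does not remove the point. Results that exist in a chart are not study data unless the plan says they will be recorded, and here it does not. The broader gaps in Section 12 are real, but this exit is one the protocol itself creates and can close. The best-interest exit is why deletion alone is not enough, and why the fix also requires recording after the drug is stopped.

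**Conclusion.** The concern holds. Followed as written, Section 10 allows avoidable loss of primary-endpoint PCR data in the Envarsus group only, with no added protection for the patient, because Section 5.3 already stops the drug.

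Neither the size nor the direction of any bias can be determined from the documents. They give no exit rate, no group split and no expected BK rate on Envarsus, and requiring complete data also selects among the controls. The unresolved range is k/n, for example 6 percentage points for three BK-negative leavers among an assumed 50 patients, or 3 points among an assumed 100. If such reactions are rare, the effect will be small. The change is worth making because it is cheap and the missing results are preventable, not because a large bias has been shown.

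**What to change.** - **Section 10:** remove the drug-related reaction from the list, so that it ends treatment only.
- **Section 5.3:** state that after Envarsus is stopped, standard-of-care BK PCR, rejection and graft status are recorded to month 12 unless the patient withdraws consent. Without this sentence, the best-interest exit could still lose the same data.
- **Section 12:** state that every converted patient is analysed in the Envarsus group, and that any BK event before exit counts as an event.

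The cost is one amendment. No tests are added, since urine and serum BK testing is already routine in the first year, and the safety stop is unchanged. The downside is that patients returned to tacrolimus stay in the Envarsus group, which dilutes the estimated effect by an amount that depends on the unknown discontinuation rate.
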